	UACR (x3)		x	x	x	x	DS	DS	DS
	Biomarkers		x	x		DS	DS		
Group	Immediate Start		x	x	x				
	Delayed Start		x	x	x	x	x	x	x

*CBC, Renal Panel, Ferritin, TSAT

** V1 if consent: CBC & eGFR panel

DS = Delayed Start ONLY

This is a two-arm, open-label, single-center, randomized controlled trial to understand the mechanisms of EIH. Participants will be randomized based on stratum of baseline level of urine albumin/urine creatinine ratios (UACR) measured on three consecutive days. The primary analysis will compare the 80 participants in the early start group to the 80 in the delayed start (DS) or waitlisted group over the first 12 weeks. All procedures will be performed as listed in the table based on study visit. Confirmatory analysis will compare the first 12 weeks to the next 12 weeks in the DS group. Accordingly, the study procedures labeled DS will be performed only in the delayed start randomized participants.

Study Intervention

Participants with CKD and anemia who meet the inclusion and exclusion criteria will be randomized to either the immediate or delayed start group. There are at least 7 study related visits in the early start group, and 11 in the waitlist group. Two consecutive days are needed to perform 24h ambulatory BP monitoring, which will be done twice in the immediate start group and 3 times in the delayed start group. Patients will receive oral iron (ferrous sulfate, 324 mg orally twice daily) if serum ferritin concentration is <100 ng/mL or transferrin saturation is <20%. If clinic BP exceeds either 179 mmHg systolic or 109 mmHg diastolic or if clinic BP raises by >20/10 mmHg compared to baseline, antihypertensive medication dose will be increased or a new antihypertensive will be added.

Participants will be identified in the renal clinic or the electronic medical record system based on estimated GFR and Hgb. At baseline, all participants will have 24-h urine Na measured to assess dietary Na intake.

Treatment Adherence

We recognize the limitations of syringe count, but we will assess treatment compliance with the study drug by performing a syringe count at each of the study visits.

Protocol for the management of anemia

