Darbepoetin will be self-administered subcutaneously at a starting dose of 0.45 µg/kg once weekly. Hgb will be targeted between 10-12 g/dL with a goal of at least 2 g/dL increment from baseline. If a patient's Hgb increases by 2 or more g/dL during any 4-week period, the darbepoetin dose will be decreased by 25%. If Hgb rise over 4 weeks is < 1g/dL and patient is not in target Hgb range the dose of darbepoetin may be increased by 25%. If Hgb change from baseline is between 1 - 2 g/dL the dose of darbepoetin will be maintained. If Hgb concentration increases to >12.0 g/dL, the drug will be withheld until Hgb concentration falls to <12 g/dL, at which time it may be restarted at a dose 25% lower than the previous dose.

In a Phase III registration trial of darbepoetin in CKD,⁸⁷ the median response time to increase in Hgb was 7 weeks. The response was defined as an increase in Hgb of ≥ 1 g/dL from baseline and Hgb ≥ 11 g/dL. The peak response was achieved at 13 weeks. Since we want to magnify the difference between groups, a 12-week treatment period appears appropriate. We expect about half of the participants to be treated for 24 weeks since the waitlisted group will be treated after 12 weeks.

Stop points

1. Stop point for severe anemia: If Hgb drops to <8 g/dL, waitlisted patients (delayed start group) will be started on EPO therapy without further delay. In the TREAT trial, where the rescue threshold was 9 g/dL, less than half (46%) of the patients in the placebo group needed at least one dose of EPO over the life of the trial ¹⁰. The target for rescue therapy is even lower in this trial and we do not expect many patients to be taken off the waitlist.

2. Stop point for uncontrolled hypertension: If clinic BP exceeds either 179 mmHg systolic or 109 mmHg diastolic, or rises by >20 mmHg/10 mmHg, antihypertensive medication dose will be increased, or a new medication added.

Safety Assessments and Variables

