- model 1: The outcome variable will be 24h ambulatory diastolic BP. The predictors will be indicator variables for group (early or late start), time (baseline and 12 weeks), stratum (UACR: none, high, very high) and all interactions. The random component of the mixed model will include subject and time. Unstructured covariance will be used with estimation of marginal means by maximum likelihood. We expect the interaction between group by time to be significant. The random coefficient analysis does not require baseline systolic BP as a covariate. If the 3-way interaction term (group x time x stratum) is significant, then results will be reported within each stratum. Confirmatory analyses will utilize change from baseline in clinic diastolic BP.
- model 2: The outcome variable will be 24h ambulatory diastolic BP. The predictors will be indicator variables for period within the delayed start group (early or late), time (baseline and 12 weeks from start of period), stratum (UACR: none, high, very high) and

all their interactions. The random component of the mixed model will include subject and time. We expect the interaction between period by time to be significant. If the 3-way interaction term is significant, then results will be reported within each stratum.

Accounting for missing data

Ambulatory BP recording, the gold-standard to assess BP, is carried out only twice during the trial in the parallel group analysis, but clinic BP measurements occur every 4 weeks. Patients who drop out but have some post-baseline measurements of clinic BP will be included in the analyses, thus minimizing loss to follow up. We will impute ambulatory BP as follows: we will use the complete data to build a model that relates the follow-up mean 24-hour ambulatory diastolic BP from the baseline 24-hour ambulatory diastolic BP and the clinic measures using repeated measures Mixed Model regression - then use the expected value from the model for the missing value - and use PROC MI (which generates maybe 5 replicate values to insert variability into the imputation) so that there is a price to pay for imputing.

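### Antihypertensive escalation can act before the week-12 ambulatory BP, so Model 1 estimates EPO plus escalation; the plan neither says so nor gives a companion estimate in mmHg

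*Combined protocol and SAP*

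**What the plan says.** **The rule.** Under Study Intervention, treatment is stepped up if clinic BP exceeds 179 mmHg systolic or 109 mmHg diastolic, or "if clinic BP raises by >20/10 mmHg compared to baseline". In those cases "antihypertensive medication dose will be increased or a new antihypertensive will be added". Stop points, item 2, repeats it: "or rises by >20 mmHg/10 mmHg, antihypertensive medication dose will be increased, or a new medication added". The wording is mandatory and covers both arms. The relative trigger does not say whether one component or both must be exceeded.

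**The timing.** Accounting for missing data states that "clinic BP measurements occur every 4 weeks", and that "Ambulatory BP recording, the gold-standard to assess BP, is carried out only twice during the trial in the parallel group analysis". Figure 2 places those two recordings at baseline and week 12.

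**The analysis.** For Model 1 (Primary Analysis), "The outcome variable will be 24h ambulatory diastolic BP". Its explanatory terms are then listed: "The predictors will be indicator variables for group (early or late start), time (baseline and 12 weeks), stratum", followed by the interactions. Antihypertensive change does not appear. The missing-data text deals with ambulatory values lost to dropout, and the intention-to-treat sentence under Safety Assessments deals with stopping the study drug.

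**Where escalation is counted.** An increase in BP medication counts as worsening of hypertension (Outcome Variables, item 2). That binary outcome is compared between groups by logistic regression, and by the McNemar test within the delayed-start group.

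**The aim.** The Primary Objective section wants the size of the BP change measured precisely, for later comparison with HIF stabilizers. Background lists antihypertensive prescribing among the reasons why EPO-induced hypertension is under-reported.

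**The concern.** The trigger is the effect under study. If EPO raises BP, more EPO patients than controls should cross it, and part of their rise will have been treated by the time the primary outcome is measured. Model 1 uses the week-12 value as recorded. It answers a legitimate question: what happens to BP when EPO is given under this protocol's BP management. It does not answer the pharmacological question of how far EPO raises BP without added drugs.

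The plan does not say which of the two it intends, for the estimate or for the 5 mmHg in the sample size. A small difference could be read as a small pressor effect of EPO when some of the rise had been treated. The binary worsening outcome would flag this but cannot return the effect in mmHg. Clinic diastolic BP, the confirmatory outcome, is subject to the same rule. So is the EPO period of the delayed-start group in Model 2.

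**Working it through.** **1. Reproduce the plan's sample size.** Inputs (Sample Size section): difference 5 mmHg, SD of change 10.3 mmHg, two-tailed, 80% power. Alpha is not stated there; 0.05 is assumed.

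- n per arm = 2 × (1.960 + 0.842)² × 10.3² / 5² = 66.6, so 67 by the normal approximation. The t-test gives 67.6, so 68, as stated.
- 68 / 0.85 = 80 per group, 160 in total, as stated.
- SE at 68 per arm = 10.3 × √(2/68) = 1.766 mmHg. Power = Φ(5/1.766 − 1.960) = Φ(0.871) = 80.8% (t-test 80.2%).

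There is almost no reserve: t-test power is below 80% at a net difference of 4.98 mmHg.

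**2. Does the trigger fire more often on EPO?** Assume the SD of clinic diastolic change equals 10.3 mmHg (the plan gives it for ambulatory BP only). The chance of a rise above 10 mmHg at one visit is 1 − Φ((10 − μ)/10.3):

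| True rise μ at that visit | Chance |
|---|---|
| 0 mmHg | 17% |
| 2.5 mmHg | 23% |
| 5 mmHg | 31% |

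It fires in both arms, and more often on EPO if EPO raises BP. Only the between-arm excess moves the contrast.

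**3. Size of the attenuation.** Net difference ≈ 5 − (share escalated on EPO − share escalated in controls) × lowering per escalation. The shares come from simulations of the week-4 and week-8 visits, with change SDs of 10.3 (diastolic) and 16.7 mmHg (systolic), part of the EPO effect already present at those visits, and a range of correlations. Lowering per escalation is assumed at 3 to 8 mmHg in 24-hour diastolic BP, with one escalation per participant.

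| Trigger read as | Controls / EPO escalated | Excess | Net at 3 mmHg | Net at 8 mmHg |
|---|---|---|---|---|
| Either component | 33–34% / 48–51% | 14–17 points | 5 − 0.14×3 = 4.58 to 5 − 0.17×3 = 4.49 | 5 − 0.14×8 = 3.88 to 5 − 0.17×8 = 3.64 |
| Both components | 10–12% / 18–23% | 8–11 points | 5 − 0.08×3 = 4.76 to 5 − 0.11×3 = 4.67 | 5 − 0.08×8 = 4.36 to 5 − 0.11×8 = 4.12 |

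With unrounded shares the lowest either-component value is about 3.7, so the ranges are roughly 3.7 to 4.6 and 4.1 to 4.8 mmHg. If a second escalation at week 8 is allowed, each lowering BP by 8 mmHg, the either-component figure falls to 3.30 mmHg.

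**4. Power at 68 per arm.** With SD held at 10.3, net 4.5 gives Φ(4.5/1.766 − 1.960) = 72%, net 4.0 gives 62%, and net 3.7 gives 55%. Escalation trims the largest rises and so narrows the week-12 spread, which returns part of the loss. Allowing for that, the most favourable simulated settings reach about 79%. The range is therefore roughly 55% to 79%; the two-escalation corner reaches 47%.

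**5. No EPO effect.** With a true effect of zero the simulated net difference is zero, so there is no bias at the null.

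**6. Can the planned imputation be reused?** As described, it predicts week-12 ambulatory diastolic BP from baseline ambulatory BP and the clinic measures; treatment group is not named. Take a true effect of 5 mmHg, a drug effect of 5 mmHg and the either-component trigger, and set post-escalation values to missing:

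| Analysis | Estimate (mmHg) | Power |
|---|---|---|
| Model 1 as planned | about 4.2 to 4.4 | 64–77% |
| Imputation without group | 3.2 to 4.1 | 22–43% (for 3.2–3.6) |
| Imputation with group | 4.8 to 5.0 | 48–66% |

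Without group, the imputed values in the two arms are drawn together and the estimate ends up further from 5 than Model 1. With group, the 5 mmHg is recovered, at a cost in precision.

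**The case against.** **Model 1 is not biased for the treatment-policy effect.** This stands. Participants are enrolled with or without antihypertensives, and escalation is part of the care under study. A reader might infer that the primary analysis is simply wrong; the documents do not support that. The gap is that the target is unstated and the no-escalation effect has no estimate.

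**Power may be intact.** This stands too. A reader might infer that the stated 80% is not delivered. The Sample Size section speaks only of a between-group difference and does not say whether escalation is included. If 5 mmHg is already net, power stays at about 80%. If all 80 per arm contributed in full, power would be 86.7% at 5 mmHg and 78.9% at 4.5 mmHg.

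**The plan does count escalation.** It does, in the binary worsening outcome, so a null mmHg result would be read beside it. That warns of treated rises but does not size them.

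**A lower bound?** A reader might take Model 1 as a guaranteed lower bound for the BP rise. That needs the excess escalation to fall in the EPO arm. "This is a two-arm, open-label, single-center, randomized controlled trial", says the protocol, and medication changes outside the trigger are not described, so the bound is expected but not proven.

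**Conclusion.** The concern holds as a gap in the target and in the supporting analysis. Escalation is mandatory, is triggered by the effect under study, can precede the week-12 recording, and has no mmHg analysis of its own. Model 1 is a valid treatment-policy analysis. It is attenuated relative to the no-escalation effect if EPO raises BP and escalation is more frequent on EPO.

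The size rests on assumptions, because escalation rates, drug effects and clinic-change SDs are not in the documents. For a 5 mmHg no-escalation effect, the loss is roughly 0.2 to 1.3 mmHg across both readings of the trigger. Power falls to roughly 55–79% if 5 mmHg is the effect without escalation, and hardly at all if it is net. The low end needs the either-component reading and an 8 mmHg drug effect together.

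**What to change.** The clinical escalation rule is left as it is. In the analysis plan:

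1. Name Model 1 as the treatment-policy primary analysis.
2. State whether the 5 mmHg is gross or net of escalation. If gross, show the effect on sample size. By the normal approximation, a net 4.5 mmHg needs 83 completers per group (83/0.85 = 98 randomized, 196 in total), and a net 4.0 mmHg needs 105 (124 randomized, 248 in total).
3. Pre-specify a supplementary hypothetical-strategy estimate. Set week-12 ambulatory BP after an escalation to missing and multiply impute it from baseline ambulatory BP, pre-escalation clinic systolic and diastolic BP including the trigger visit, UACR stratum and treatment group. Group must be added to the imputation model now described. Use more than 5 imputations. Because the trigger depends on recorded clinic BP, missing at random is plausible for trigger-driven changes.
4. Record the date of each antihypertensive change and tabulate escalation by arm.
5. State how the relative trigger is read (one component or both), so that escalations can be classified consistently.
6. Do not put post-randomization medication into Model 1 as a covariate.

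Cost: wording, dates of medication changes in the case record, and one extra analysis on BP data already planned. The supplementary estimate depends on its imputation model and is less precise than Model 1, which is why it should support the primary analysis and not replace it.

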On the other hand, HIF stabilizers may raise EPO to more physiologic levels, reduce crosstalk with vascular EPO-receptors, and mitigate hypertension. A 2014 study demonstrated in a rodent model that compared to EPO, treatment with HIF-stabilizer molidustat corrected anemia associated with subtotal nephrectomy. However, in contrast to EPO, molidustat reduced systolic BP in a dose-dependent manner⁸². The authors postulate that anti-inflammatory and anti-fibrotic effects of the drug on the kidney may be operative. This study further illustrates that increment in Hgb can be dissociated from an increment in BP. Human data are available but are thus far inadequate to address the question of risk for or protection from incident hypertension with HIF stabilizers ⁸³⁻⁸⁶.

RESEARCH PROTOCOL AND TRIAL DESIGN

Overall trial design and plan

To test the notion that EPO treatment in anemic patients with CKD and stage 1 or less hypertension that is treated or untreated with antihypertensive medications will raise BP, we propose a randomized controlled trial with a “waiting-list design” as shown in **Figure 2**. In this design, half of the patients are treated immediately with EPO and the other half are put on a waiting list for 12 weeks, after which they begin treatment. Ultimately, the waitlisted patients are exposed to the intervention, thus serving as their own controls. The design allows between-group comparison by comparing responses in the parallel groups over 12 weeks and within-group comparison for the waitlist group in the second 12 weeks compared to the first 12 weeks. Titration of the dose of EPO will occur every 4 weeks to manage anemia as detailed below. The effect of EPO on BP will be assessed by change in diastolic ambulatory BP measured over 24 hours at baseline and again at 12 weeks in both groups and at 24 weeks in the waitlisted group. At baseline and every 4 weeks thereafter, we will also evaluate changes in clinic BP and albuminuria. At baseline and 4 weeks after intervention, we will measure endothelial function, and collect blood for biomarkers. The biomarkers we will be analyzing are renin, aldo, ET-1, catecholamine, ADMA, and urine nitrates and nitrites.

Figure 2: Trial design and study process

Visit		1	2-3	4	5	6-7	8	9	10
Measurement		Consent	Baseline	Week 4	Week 8	Week 12	Week 16	Week 20	Week 24
PROC	FMD		x	x		DS	DS		
HTN	24h-ABPM		x			x			DS
	Clinic BP	x	x	x	x	x	DS	DS	DS
Labs	24h-urine		x			x			DS
	Blood labs*	x**	x	x	x	x	DS	DS	DS

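### The darbepoetin titration rules mix the 4-week Hgb change with the change from baseline and set no precedence, so some Hgb paths meet two incompatible mandatory dose instructions

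*Combined protocol and SAP*

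**What the plan says.** *Protocol for the management of anemia* opens with the aim: "Hgb will be targeted between 10-12 g/dL with a goal of at least 2 g/dL increment from baseline". Four dose rules follow, on three different scales.

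- **Decrease (4-week change, mandatory):** "Hgb increases by 2 or more g/dL during any 4-week period, the darbepoetin dose will be decreased by 25" per cent.
- **Increase (4-week change plus target range, permissive, a 25% step):** "If Hgb rise over 4 weeks is < 1g/dL and patient is not in target Hgb range the dose of darbepoetin may be increased".
- **Maintain (change from baseline, mandatory):** "If Hgb change from baseline is between 1 - 2 g/dL the dose of darbepoetin will be maintained".
- **Withhold (absolute level, mandatory):** "If Hgb concentration increases to >12.0 g/dL, the drug will be withheld until Hgb concentration falls to <12 g/dL".

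*Overall trial design and plan* sets the timing: "Titration of the dose of EPO will occur every 4 weeks to manage anemia as detailed below". Figure 2 shows immediate-start treatment at baseline, week 4 and week 8, so week 8 is that arm's last titration before the week-12 ambulatory BP. Entry Hgb is 8 to 10 g/dL (*Inclusion Criteria*). Delayed-start patients receive no drug before week 12 unless Hgb falls below 8 g/dL (*Stop points*). No section ranks the four rules or says what baseline means for a patient who starts drug at week 12.

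**The concern.** One rule measures the rise over the last 4 weeks and another measures it from baseline. The two agree only while those quantities are equal. Once they differ, a patient can satisfy the condition for a required cut and the condition for a required hold at the same visit. The site cannot follow both, and a monitor cannot say which choice is a deviation.

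The drug is the intervention under test and the trial is open-label, so dosing should not depend on how a sentence is read. The decrease rule is also the plan's response to a rapid Hgb rise, so the ambiguity touches safety handling as well as consistency of exposure.

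**Working it through.** The plan gives no figure on this point to reproduce. The check applies the four rules literally.

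**Notation (g/dL).** B = baseline Hgb, P = Hgb 4 weeks earlier, C = current Hgb. The 4-week change is d4 = C − P. The change from baseline is dB = C − B. Hence P − B = dB − d4.

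**Rules.** Decrease if d4 ≥ 2. May increase if d4 < 1 and C is outside 10–12. Maintain if 1 ≤ dB ≤ 2. Withhold if C > 12.0.

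**Week 4.** Here P = B, so d4 = dB. Decrease and maintain meet only when the rise is exactly 2.0 and the limit of 2 counts as inside the range (for example 9.0 to 11.0). Increase and maintain cannot meet, because the same number would have to be below 1 and at least 1.

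**Week 8, decrease against maintain.** Both apply when d4 ≥ 2 and dB ≤ 2, so P − B = dB − d4 ≤ 0. The week-4 Hgb must be at or below baseline. Example 9.0, 8.5, 10.6:
- d4 = 10.6 − 8.5 = 2.1, so the dose must be decreased.
- dB = 10.6 − 9.0 = 1.6, so the dose must be maintained.
- C = 10.6 is below 12, so the withhold rule does not settle it.

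**Week 8, increase against maintain.** Example 8.0, 8.8, 9.4:
- d4 = 9.4 − 8.8 = 0.6 and 9.4 is below 10, so an increase is permitted.
- dB = 9.4 − 8.0 = 1.4, so the dose must be maintained.

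This overlap needs C < 10 and C ≥ B + 1, hence B < 9.0. On a 0.1 g/dL scale with rising or flat Hgb, it can occur for every baseline from 8.0 to 8.9. Holding the dose complies with both sentences, because one of them only permits.

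**Delayed-start arm.** Example: 9.0 at week 0, 8.3 at week 12 (drug start), 10.4 at week 16.

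| Meaning of baseline | d4 | dB | Rules met |
|---|---|---|---|
| Week 0 | 10.4 − 8.3 = 2.1 | 10.4 − 9.0 = 1.4 | Decrease and maintain |
| Week 12 | 2.1 | 10.4 − 8.3 = 2.1 | Decrease only |

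**Size of the dose difference.** Set the starting weekly dose to 1 unit and assume weekly dosing as planned.
- No change before week 8: hold gives 12 × 1 = 12; decrease gives 8 × 1 + 4 × 0.75 = 11. The difference is 1/12 = 8.3%.
- Permitted 25% increase taken at week 4: hold gives 4 + 8 × 1.25 = 14; decrease gives 4 + 4 × 1.25 + 4 × 0.9375 = 12.75. The difference is 1.25/14 = 8.9%.

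Within weeks 8 to 12 alone, the weekly dose differs by 25%.

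**The case against.** The strongest reply has four parts.

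1. The true conflict needs an unusual path: no net rise by week 4, then 2 g/dL or more in the next 4 weeks. The decrease rule can be read as a rate limit that applies whatever the cumulative change. The rarity argument stands as a judgement, though the documents give no Hgb distribution to test it. The rate-limit reading is sensible, but the text does not state it, and the maintain rule carries no exception.

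2. The slow-responder path (8.0, 8.8, 9.4) sets a permission against an instruction, so it is not a contradiction. This stands. It is ambiguous wording only.

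3. The stated aim, "with a goal of at least 2 g/dL increment from baseline", is a goal and not an order to keep raising the dose. The same section reports a peak response at 13 weeks in the cited phase III trial, so Hgb may still climb on a held dose. This stands too. A reader might infer that holding at +1 to +2 g/dL contradicts the goal, but the text does not go that far. It leaves unexplained how the two fit together, for example for a patient at 8.0, 9.2, 9.2, who has reached neither goal nor target range.

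4. The background section on hemopoietic versus hypertensive effects says the BP rise does not depend on dose, so a modest dose difference may not matter for BP. That section also cites a study in which Hgb change correlated with diastolic BP change (r = 0.42), so the documents leave the question open. Either way, the primary contrast is drug against no drug, and dose variation within the treated arm does not bias it.

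**Conclusion.** The point holds in a limited form. Two mandatory instructions can apply to the same patient at the same visit, and nothing in the plan chooses between them. Among patients dosed on schedule, the effect before the primary measurement is confined to the week-8 titration in the immediate-start arm, apart from the boundary case of exactly +2.0 g/dL at week 4. After week 12, the undefined baseline adds a second source of conflict in the delayed-start arm.

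The consequence is inconsistent dosing and inconsistent handling of a rapid Hgb rise. In an affected immediate-start patient it amounts to about 8% of the cumulative 12-week dose, or about 9% if the dose was raised at week 4. These figures assume weekly dosing as planned and a single 25% step at week 8. The share of patients affected cannot be computed from the documents.

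A reader might infer that unclear dosing undermines the week-12 comparison or its power. The documents do not support that: the randomized drug-versus-no-drug contrast is unbiased by it, and the 68 completers per group (80 randomized) are unaffected.

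**What to change.** Reconcile the titration sentences into one set of rules in which every combination of current Hgb, 4-week change and change from baseline leads to a single instruction. The text should:

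- state whether the 4-week change or the change from baseline takes precedence when they point to different actions;
- say whether the limits of 1 and 2 g/dL are included, which settles the week-4 boundary case;
- define baseline for dosing in each arm, including delayed-start patients who begin drug early under the severe-anemia stop point;
- make clear whether the permitted increase can apply to a patient who also meets the maintain rule;
- explain how holding the dose at +1 to +2 g/dL relates to the stated goal.

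The clinical content of each rule is for the sponsor to decide. The cost is protocol wording. The visit schedule, randomization, sample size and analysis models need no change.
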